## **9 STATISTICS**

Detailed methodology for summary and statistical analyses of the data collected in this study will be documented in a [Statistical Analysis Plan \(SAP\)](#), which will be maintained by the Sponsor. The SAP may modify the plans outlined in the protocol; however, any major modifications of the primary endpoint definition and/or its analysis will also be reflected in a protocol amendment.

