## 9.3 Analysis Populations

### 9.3.1 *Modified Intent-to-Treat Population*

The Modified Intent-to-Treat (mITT) population is defined as all patients who receive treatment with both mocetinostat and durvalumab on this study.

The primary efficacy analyses of the primary and secondary efficacy endpoints will be performed in the mITT population. In addition, the mITT population will be used in making decisions to expand the study to the next stage of enrollment (to up to 100 patients).

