### 9.3.2 *Clinical Activity Evaluable Population*

In order to be considered eligible for the clinical activity evaluable population, the patient must have at least one on-study disease assessment or discontinue from treatment for PD. Patients who discontinue treatment prior to the first on-study disease assessment for an AE, toxicity, or withdraw consent are considered non-evaluable for disease assessment and will not be part of the clinical activity evaluable population.

This population will be used to present tumor responses as well as to make decision on the Predictive Probability design.

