4.0 Introduction

This SAP describes the statistical methods to be used during the analysis and reporting of data collected under Mirati Therapeutics, Inc. Protocol 0103-020.

This SAP should be read in conjunction with the study protocol and case report form (CRF). This version of the plan has been developed using the protocol dated 10 May 2017 and CRF dated 06SEP2016. Any further changes to the protocol or CRF may necessitate updates to the SAP.

The SAP is to be developed in two stages. An initial SAP, known as SAP1, is finalized based on the current protocol and CRF, so that programming may be created. Changes following approval of SAP1 will be tracked in the SAP Change Log. A final version of the SAP, known as SAP2, will be issued prior to database lock.

Each version of the SAP requires approval by the project manager and the sponsor.

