7.2 Modified Intent-to-Treat Population

The Modified Intent-to-Treat (mITT) population is defined as all patients who receive treatment with both mocetinostat and durvalumab on this study.

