7.3 Clinical Activity Evaluable Population

In order to be considered eligible for the clinical activity evaluable population, the patient must have at least one on-study disease assessment or discontinue from treatment for PD. Patients who discontinue treatment prior to the first on-study disease assessment for an AE, toxicity, or withdraw consent are considered non-evaluable for disease assessment and will not be part of the clinical activity evaluable population.

This population will be used to present tumor responses as well as to make decision on the Predictive Probability design.

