12.5 Efficacy Analyses

12.5.1 ORR, Best Overall Response and CBR

Descriptive statistics (frequency and percentage) for ORR, CBR and of best overall response (CR, PR, SD, PD) based on the Response Assessments by the Investigator and the exact 95% Clopper-Pearson confidence interval (SAS® PROC FREQ) of the response rate will be presented by phase and by dose level/cohort and overall within each phase. An exact test (SAS® PROC FREQ) for single proportion (two-sided $\alpha=5\%$) will be performed to test H_0 : ORR $\leq 5\%$ against H_1 : ORR $> 5\%$ in cohorts 1, 3, and 4 and to test H_0 : ORR $\leq 27\%$ against H_1 : ORR $> 27\%$ in cohort 2, for phase 2 of the study. Patients who cannot be assessed for response will be counted as non-responders. Descriptive statistics (frequency and percentage) for CR and PR rate will be presented by phase, dose level/cohort, and overall within each phase. In addition, exact binomial 95% CIs for the percentage will be displayed for CR and PR rate, respectively.

The primary analyses will be conducted in the clinical activity evaluable population. Supportive analyses will be presented in the mITT population.

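### SAP 12.5.1 and Protocol 9.3.1 name different primary analysis populations for ORR and clinical benefit rate

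*SAP*

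**What the plan says.** Protocol 9.3.1: "The primary efficacy analyses of the primary and secondary efficacy endpoints will be performed in the mITT population". ORR is the primary Phase 2 endpoint and CBR a listed secondary one, so both fall under that sentence.

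SAP 12.5.1, which covers ORR, best overall response and CBR: "The primary analyses will be conducted in the clinical activity evaluable population. Supportive analyses will be presented in the mITT population". Best overall response is not a listed endpoint; it matters here as the basis of ORR. SAP 12.5.2 keeps PFS and OS in mITT.

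The SAP is not working from an older protocol: "This version of the plan has been developed using the protocol dated 10 May 2017 and CRF dated 06SEP2016". Protocol section 9 lets the SAP modify the planned analyses, with a limit: "any major modifications of the primary endpoint definition and/or its analysis will also be reflected in a protocol amendment".

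The two sets are defined as follows.
- mITT (SAP 7.2, matching the protocol): "all patients who receive treatment with both mocetinostat and durvalumab on this study".
- Clinical activity evaluable (Protocol 9.3.2, SAP 7.3): at least one on-study disease assessment, or treatment stopped for PD. "Patients who discontinue treatment prior to the first on-study disease assessment for an AE, toxicity, or withdraw consent are considered non-evaluable". On its use, SAP 7.3 says: "This population will be used to present tumor responses as well as to make decision on the Predictive Probability design". Protocol 9.3.2 assigns the same use. Neither calls this set primary.

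**The concern.** Two controlling documents give opposite answers to which population carries the primary analysis of the primary endpoint. SAP 7.2 repeats the mITT definition but leaves out the protocol's sentence making it primary, and does not flag a change.

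The choice affects the result. The evaluable set leaves out treated patients who stop early for toxicity, an AE or withdrawn consent. In mITT these patients stay in the denominator as non-responders under the SAP 12.5.1 rule for patients who cannot be assessed. That rule cannot reach patients who have already been removed from the set. The first on-study scan falls about eight weeks after Cycle 1 Day 1, so there is time for such losses to build up. In an open-label study, leaving the primary set unresolved until responses are known allows a choice between two analyses that can disagree near the significance threshold.

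**Working it through.** **1. Reproduce the plan's own figures.** Two-stage rejection probability = sum over Stage 1 counts x at or above the continuation bound of P(X1 = x) × P(X2 ≥ r − x). The inputs are from Protocol 9.1.2.
- Cohorts 1, 3, 4 (continue at ≥1/9, go at ≥3/17, p0 = 5%, p1 = 30%): Type 1 error 0.0466, power 0.9045.
- Cohort 2 (continue at ≥5/17, go at ≥18/44, p0 = 27%, p1 = 50%): Type 1 error 0.0303, power 0.9018.

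Both match. These rules are counted in evaluable patients and do not depend on which set is primary for the final test.

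**2. Threshold of the final test.** SAP 12.5.1 specifies an exact single-proportion test, two-sided α = 5%. I take p = 2 × P(X ≥ x | n, p0). The smallest counts that pass are 19/44 (2 × 0.0150 = 0.030) and 4/17 (2 × 0.0088 = 0.018).

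**3. Same responders, L early losses added as non-responders.** The documents give no value for L, so it is assumed. Intervals are Clopper-Pearson 95%.

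| Cohort | Responders/n | L | ORR | 95% CI | Two-sided p |
|---|---|---|---|---|---|
| 2 | 19/44 | 0 | 43.2% | 28.3–59.0% | 0.030 |
| 2 | 19/46 | 2 | 41.3% | 27.0–56.8% | 0.05005 |
| 2 | 19/47 | 3 | 40.4% | 26.4–55.7% | 0.063 |
| 2 | 20/44 | 0 | 45.5% | 30.4–61.1% | 0.013 |
| 2 | 20/48 | 4 | 41.7% | 27.6–56.8% | 0.039 |
| 2 | 20/49 | 5 | 40.8% | 27.0–55.8% | 0.0501 |
| 1, 3, 4 | 4/17 | 0 | 23.5% | 6.8–49.9% | 0.018 |
| 1, 3, 4 | 4/22 | 5 | 18.2% | 5.2–40.3% | 0.044 |
| 1, 3, 4 | 4/23 | 6 | 17.4% | 4.9–38.8% | 0.052 |

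At 19 responders, two losses put the result on the line and three put it clearly past. Three losses is 3/47 = 6.4%. The nearest documented figure is 29/444 = 6.5% stopping durvalumab monotherapy for AEs at any time (Protocol 1.3.3). That indicates an order of magnitude only; it is not an early-loss rate for the combination.

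**4. The direction can reverse.** The sets are not nested. A patient who stops for PD in the seven-day lead-in, before durvalumab, is evaluable but not in mITT. With k such patients, mITT n = 44 − k + L. For k = 1 and L = 3, n = 46 and p = 0.05005. For k = 1 and L = 0, 18/44 = 40.9% becomes 18/43 = 41.9% in mITT.

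**5. One-sided reading.** The hypotheses are written in one direction beside a two-sided α. At one-sided 0.05, 19/47 (p = 0.032) and 19/49 (0.0485) pass, and 19/50 (0.059) is the first to fail.

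**6. Power cost of mITT.** Assumptions: p1 holds in evaluable patients, Stage 1 rule kept, losses accrue until 44 or 17 patients are evaluable, critical value recomputed at each mITT n.

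| Assumed loss | 0% | 5% | 10% | 20% |
|---|---|---|---|---|
| Cohort 2 | 0.85 | 0.79 | 0.71 | 0.52 |
| Cohorts 1, 3, 4 | 0.79 | 0.79 | 0.79 | 0.74 |

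The 0% column is the evaluable-set test.

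**The case against.** The SAP's choice has some protocol support. The Phase 2 stages are sized and decided in evaluable patients. Amendment 2 added Protocol 9.3.2, which gives the evaluable set the presentation of tumor responses. Protocol 9.3.1 may therefore be text that the amendment left unaligned. That is a fair reading of how the mismatch arose, but it does not remove it: 9.3.2 never calls the evaluable set primary, and 9.3.1 still names mITT. It does mean that the documents alone do not show which population was intended.

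The test reversals are near-threshold cases on assumed losses, and they depend on the two-sided reading. That stands. So does the power cost: mITT lowers Cohort 2 power without any re-sizing.

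A reader might infer that the evaluable-set test inflates the Type 1 error. That needs p0 to be an mITT-scale rate. The durvalumab rates in Protocol 1.1.1 were computed in response-evaluable patients, and the design is sized in evaluable patients, so the documents do not support it.

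A reader might also see a second conflict in the Protocol 9.3.1 statement that "the mITT population will be used in making decisions to expand the study to the next stage of enrollment", since 9.3.2 gives the Predictive Probability decisions to the evaluable set. The 9.3.1 sentence goes on to mention up to 100 patients, a figure used elsewhere only for the optional expansion of Cohorts 3 and 4, so it is already largely confined to that step.

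**Conclusion.** The contradiction is real for ORR and CBR, and neither the SAP's latitude to modify plans nor Protocol 9.3.2 resolves it. What is unsettled is which estimate, interval and test is the primary result. The evaluable-set ORR is expected to be the higher, because the patients it drops count as failures in mITT and can accrue over about eight weeks, while the opposing lead-in case arises essentially within seven days. This is an expectation, not a certainty.

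The effect is modest and conditional. On three assumed losses, a Cohort 2 result at the two-sided threshold falls by 43.2 − 40.4 = 2.8 percentage points and no longer passes; read one-sided at 0.05 it still does. Cohorts 1, 3 and 4 are robust up to five losses. It would go too far to say that the study's decisions are compromised: the go rules of 18/44 and 3/17 are unchanged, and both populations are to be reported. Should-fix.

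**What to change.** Before SAP2 is issued and the database is locked, make both documents name one primary population for ORR and CBR, with best overall response following ORR.

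- **Default:** conform SAP 12.5.1 to Protocol 9.3.1. Make mITT primary, apply the non-responder rule already in SAP 12.5.1 to all mITT patients, and report the evaluable set as supportive. Keep the evaluable set for the Predictive Probability decisions.
- **Alternative:** if the sponsor wants the evaluable set as primary, amend Protocol 9.3.1 as section 9 requires, and report mITT alongside.

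Either route is a wording change and needs no new data. The default has a price: a somewhat lower primary ORR, patients who leave for reasons unrelated to the drug counted as failures, and lower Cohort 2 exact-test power (about 0.71 against 0.85 at an assumed 10% loss). The cost in Cohorts 1, 3 and 4 is small. The alternative keeps the power, but its headline ORR then describes only patients who reached a scan or stopped for PD.

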12.5.2 Time-to-event Variables

Time-to-event variables, DR, PFS, and OS, will be summarized by phase and by dose level/cohort and overall within each phase, descriptively using the Kaplan-Meier estimate (SAS® PROC LIFETEST). The median, 25th percentile, and 75th percentile of DR, PFS, and OS and their two sided 95% CIs using the complementary log-log transformation method ([Collett, 1994](#)) will be calculated where appropriate. In addition, minimum and maximum will also be displayed. Kaplan-Meier plots will be provided for DR, PFS, and OS.

Sponsor: Mirati Therapeutics, Inc.

Protocol no: 0103-020

DR, PFS, and CBR will be based on the Response Assessments by the Investigator. DR will be conducted in both the clinical activity evaluable and mITT populations. PFS and OS will be conducted in the mITT population.

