The populations included in Cohorts 3 and 4, who have had disease progression during treatment with a checkpoint inhibitor, represent a potential unmet medical need. For this reason, if results in Stage 2 of enrollment are of high interest, enrollment may be expanded to as many as 100 patients total in each cohort to narrow the 95% confidence interval (CI) around the ORR point estimate and more fully characterize the secondary endpoints in the population of interest.

In order to be part of the clinical activity evaluable population, the patient must have at least one on-study disease assessment or discontinue from treatment for PD prior to this assessment. Patients who

Sponsor: Mirati Therapeutics, Inc.

Protocol no: 0103-020

discontinue treatment prior to the first on-study disease assessment for an AE, toxicity, or withdraw consent are considered non-evaluable for disease assessment. These patients will not be part of the clinical activity evaluable population.

Disease response and progression as documented by the investigator in the CRF will be the basis for patient management and study expansion decision making. Unconfirmed objective responses recorded in the CRF may be used as an initial basis for expansion of study enrollment; however, follow-up evaluations on patients with unconfirmed responses must continue to support the decision to continue to the full number of patients to be included in the next stage. Central radiology review for disease response and progression may be added to the study during Stage 2. If this occurs, central review of all radiologic assessments performed in the study will be expected (including retrospective review of patients enrolled in Stage 1), and central radiology review for disease response will be the basis for the primary statistical analyses to estimate the ORR and its confidence interval, as well as the DR and PFS.

Study treatment will continue until disease progression, unacceptable AEs, patient refusal, or death.

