8.1.1 Objective Response Rate ORR)

Objective disease response will be categorized in accordance with RECIST v1.1. ORR is defined as the proportion of patients documented to have a confirmed CR or PR. If central review of disease response is undertaken, ORR as reported by the central radiology review laboratory will be used to calculate ORR and the exact binomial 95% CIs. ORR as reported by the investigator will be used in study expansion and decision making (PPD design).

Sponsor: Mirati Therapeutics, Inc.

Protocol no: 0103-020

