8.1.4 Duration of Response (DR)

DR is defined as the time in days from date of the first documentation of objective response (CR or PR) to the first documentation of objective progression of disease (PD) or to death due to any cause in the absence of documented PD (i.e., min [PD date, death date] – date of the first observation of response +1). Duration of response will only be calculated for the subgroup of patient achieving a Best Overall Response of CR or PR and will be presented for responses assessed by both central review and investigator's assessment.

Censoring rules will be applied to DR:

- Event time will be censored on the date of the last evaluable assessment documenting response for:
 - Patients on-study and progression-free at the time of an analysis;
 - Patients who have PD or death on study after ≥ 2 consecutive missed tumor assessments (i.e., >12 weeks + 14 days after the last on-study disease assessment);
 - Patients given alternative cancer treatment prior to PD or death on-study.
- Patients who die on-study after ≥ 2 consecutive missed tumor assessments (i.e., >12 weeks + 14 days after the last on-study disease assessment) will have their event time censored on the date of the last evaluable assessment documenting response.

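### If central radiology review is added, SAP 12.5 still bases ORR, DR and PFS on investigator reads, contrary to SAP 6.2 and the protocol

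*SAP*

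**What the plan says.** Central review is optional. SAP 6.2 says: "Central radiology review for disease response and progression may be added to the study during Stage 2". If it is added, the same section states that "central radiology review for disease response will be the basis for the primary statistical analyses to estimate the ORR and its confidence interval", and continues "as well as the DR and PFS". It also expects all scans to be reviewed, including those of Stage 1 patients retrospectively. Protocol 3.2 and the protocol's Study Summary say the same.

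For ORR the rule is repeated in SAP 8.1.1: "If central review of disease response is undertaken, ORR as reported by the central radiology review laboratory will be used to calculate ORR". Protocol 9.4.1 agrees, and gives the investigator's ORR two uses: expansion decisions and supportive analyses. For DR, SAP 8.1.4 says that results "will be presented for responses assessed by both central review and" investigator assessment, without saying which is primary.

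The section that specifies the efficacy analyses reads differently. SAP 12.5.1 presents ORR, CBR and best overall response (BOR) "based on the Response Assessments by the Investigator and the exact 95% Clopper-Pearson confidence interval". SAP 12.5.2 says "DR, PFS, and CBR will be based on the Response Assessments by the Investigator". Neither mentions central review.

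**The concern.** The SAP prepares for central data: section 8.1 gives dating rules for central reads, and Protocol 7.2 describes how images would reach the review vendor. Section 12.5 then gives those data no place. An analyst following 12.5 would build the primary ORR, DR and PFS tables from the reader to whom Protocol 9.4.1 gives only a supportive role in the ORR analysis.

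The reader matters here because the study is open-label with no randomized comparison. Central review would arrive during Stage 2, after investigator-read responses have already driven the decision to continue. Protocol 7.2 also lets investigators hold back a conclusion of progression when a lesion change may be transient, so DR and PFS can depend on the reader as well as ORR. At stake are the reported ORR, its confidence interval, the exact test, and the DR and PFS estimates.

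**Working it through.** **Step 1. Compare the instructions, assuming central review is added.**

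| Item | SAP 12.5 | Elsewhere | Conflict |
|---|---|---|---|
| ORR and its CI | Investigator (12.5.1) | Central primary (SAP 6.2, 8.1.1; Protocol 3.2, 9.4.1) | Yes |
| Exact test of ORR | Names no reader; the sentence before it uses the investigator | Belongs to the ORR analysis (Protocol 9.4.1) | Yes, by inference |
| DR | Investigator (12.5.2) | Central primary (SAP 6.2, Protocol 3.2); both readers (SAP 8.1.4) | Yes |
| PFS | Investigator (12.5.2) | Central primary (SAP 6.2, Protocol 3.2) | Yes |
| BOR | Investigator (12.5.1) | No reader named | Not directly, but a central ORR needs a central BOR |
| CBR | Investigator (12.5.1, 12.5.2) | No reader named | No |
| Stage and expansion decisions | Not covered | Investigator (SAP 6.2, 8.1.1; Protocol 3.2, 9.4.1) | No |

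If central review is not added, only investigator reads exist and every row is consistent.

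**Step 2. Reproduce the design figures, to see whether they are touched.** The inputs are in Protocol 9.1.2 and SAP 6.3. With stage sizes n1 and n2, continuation at r1 or more responses and success at r or more in total:

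- P(early stop) = P(X1 < r1)
- P(success) = sum over x1 ≥ r1 of P(X1 = x1) × P(X2 ≥ r − x1)

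Cohorts 1, 3 and 4 (9 then 8 patients; at least 1, then at least 3; 5% against 30%): early stop 0.95^9 = 0.6302, Type 1 error 0.0466, power 0.9045. The plan states 0.63, 0.0466 and 0.9045.

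Cohort 2 (17 then 27; at least 5, then at least 18; 27% against 50%): 0.4977, 0.0303 and 0.9018. The plan states 0.50, 0.0303 and 0.9018.

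All match. These rules run on investigator reads, so the conflict leaves them alone.

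**Step 3. Illustrate what one discordant read does to the reported result.** The documents give no discordance rate, so the counts below are assumptions. The test is exact binomial at two-sided 5% (Protocol 9.4.1, SAP 12.5.1). I take the two-sided p-value as twice the upper tail P(X ≥ x), since the documents state no convention.

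- n = 17 against 5%, 4 responders: ORR 4/17 = 23.5%, Clopper-Pearson 6.8–49.9%, p = 2 × 0.0088 = 0.018.
- n = 17 against 5%, 3 responders: ORR 3/17 = 17.6%, 3.8–43.4%, p = 2 × 0.050253 = 0.101.
- n = 44 against 27%, 19 responders: p = 2 × 0.0150 = 0.030. With 18: p = 2 × 0.0317 = 0.063.

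At n = 17 one read is worth 1/17 = 5.9 percentage points. The step from 4 to 3 also changes the decision on a one-sided reading: the tails are 0.0088 and 0.0503, on opposite sides of both 0.025 and 0.05.

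**Step 4. The 100-patient expansion.** If 5 of 30 investigator responses were not upheld (an assumption), the estimate moves from 30% (21.2–40.0%) to 25% (16.9–34.7%). Both intervals are in Protocol Table 14 and reproduce.

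**The case against.** The sponsor can say that the conflict is dormant, because central review may never be added and 12.5 is then right. The SAP describes itself as supplementing the protocol and is to be read with it. SAP 4.0 foresees a final version before database lock. Protocol section 9 requires major changes to the primary analysis to appear in a protocol amendment, so without one the protocol has already fixed the primary reader. The table shells are a separate document and may handle this correctly.

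Much of that stands. It limits the point to a conditional one, and it weakens any inference that the sponsor would be free to pick the reader after seeing both sets of results: the protocol names the central reader. But no text says that 6.2 or 8.1.1 overrides 12.5, and 12.5 is the section specific to the analyses. The final SAP and the amendment rule give a place to remove the conflict; they do not remove it.

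Two stronger readings are tempting, and the documents do not support them. A reader might infer that CBR and BOR are also assigned to central review. SAP 6.2 and Protocol 3.2 name only ORR, DR and PFS, and SAP 8.1.1 and Protocol 9.4.1 name only ORR. A reader might also infer that one discordant central read could overturn the 3-of-17 or 18-of-44 rule. Those rules use investigator responses in every version of the text. Nor does the planned test change at those thresholds: the doubled p-values are 0.101 for 3 of 17 and 0.416 for 2, and 0.063 for 18 of 44 and 0.124 for 17, so none rejects.

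**Conclusion.** The inconsistency is real for ORR with its confidence interval and exact test, for DR and for PFS, and it takes effect only if central review is added. It lies within the SAP (12.5 against 6.2, 8.1.1 and, for DR, 8.1.4) and between SAP 12.5 and Protocol 3.2 and 9.4.1. No design figure, stage rule or expansion decision changes.

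Its numerical size depends on how often the readers disagree, which the documents do not say. The step from 4 to 3 responders in 17 shows that a single disagreement can be enough to change the reported test. It is not a forecast. CBR is left without a stated reader for the central-review case, which is a gap and not a contradiction.

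**What to change.** Add a conditional sentence to SAP 12.5.1 and to 12.5.2. If central review is performed, the primary ORR (with its CI and exact test), DR and PFS use central reads for all patients, including Stage 1 retrospectively, and the investigator versions are supportive. If it is not performed, investigator reads are primary. State that stage and expansion decisions remain investigator-based in both cases.

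Then make three smaller alignments:

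- In 8.1.4, make the two-reader presentation of DR conditional on central review, and say which reader is primary.
- Derive the BOR behind the central ORR from central reads.
- State the reader for CBR; this is the sponsor's choice, since no section assigns it to central review.

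The cost is SAP wording and a second set of table shells, with no data beyond the optional review. The final SAP version before database lock is a natural place for it. If the sponsor instead wants investigator reads to be primary in all cases, that would be a major change to the primary analysis, and Protocol section 9 calls for a protocol amendment.
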